3.3.1 COVID-19-related Risks and Risk Mitigation Measures Where Applicable

The following risks and risk mitigating measures apply to any part of the study conducted during the coronavirus disease 2019 (COVID-19) pandemic. The study includes several features to mitigate this risk:

- The study sites have implemented standard operating procedures for risk mitigation as described in [Section 3.3.1.2](#).
- The protocol implements severe acute respiratory syndrome coronavirus 2 (SARS-CoV-2) testing as shown in [Table 2-1](#) in order to prevent randomization of participants with active COVID-19 infection and to ensure participant safety and study integrity.

3.3.1.1 Investigational Product-related Risk

At this time, BMS is tracking and accumulating data on COVID-19 and its potential effects on participants taking BMS-986259 and other investigational products (IPs). The data are analyzed on a regular basis. Based on its properties and mechanism of action, BMS-986259 is not believed to be implicated in COVID-19 infection and symptomology. The risk of COVID-19 in participants taking BMS-986259 is still unknown due to insufficient clinical data.

3.3.1.2 General COVID-19-related Risk Mitigation Measures

General risk mitigation for COVID-19 will be implemented in accordance with the sites' local prevention control procedures and relevant governmental and Institutional Review Board (IRB)-associated requirements. Such measures aim to minimize prevalence and transmission of SARS-CoV-2 among site staff and participants and include distancing, sanitization, use of personal protective equipment, and testing.

[figure not shown]
Participants found to test positive for SARS-CoV-2 after enrollment in the study will be treated according to site standard practice and in accordance with local and national regulations. In such cases, treatment with BMS-986259 will be discontinued as described in [Section 8](#).

The risk mitigation measures are part of the protocol-specific informed consent form (ICF), and when and where applicable, will be amended based on emerging guidance.

4 OBJECTIVES AND ENDPOINTS

Table 4-1: Objectives and Endpoints

Objectives	Endpoints

Primary
 
 • To establish safety & tolerability of BMS-986259 when initiated in-hospital in participants stabilized after an admission for ADHF 	
 • Incidence of clinically relevant hypotension, defined as: 
 – Supine SBP < 85 mmHg (confirmed by repeat measurement within 30 minutes), regardless of symptoms of hypotension OR – Supine SBP < 90 mmHg (confirmed by repeat measurement within 30 minutes) AND symptoms of hypotension

Secondary
 
 • To evaluate serum PK parameters in participants with HF 	
 • PK parameters of BMS-986259: 
 – C_{max}, T_{max}, and AUC(TAU) on Day 1 and Day 5 – C_{trough}

Abbreviations: [REDACTED] ADHF = acute decompensated heart failure; AUC(TAU) = area under the concentration-time curve in one dosing interval; BMS = Bristol-Myers Squibb; BP = blood pressure; C_{max} = maximum observed concentration; C_{trough} = trough concentration; [REDACTED] HF = heart failure; IV = intravenous; [REDACTED] PK = pharmacokinetic; [REDACTED] T_{max} = time of maximum observed concentration.

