Table 2-2: On-Treatment and Follow-up Procedural Outline (CV019010)

Procedure	Randomization D1 ^a	D 2	D 3	D 4	D 5	D 6	D 7 ^b	D 8 Visit ^c	D 9 ^b	D 10	D 11 ^b	D 12	D 13 ^d	D14 End of Study Visit c,d,e	D30 (± 2 days) Follow -Up Visit ^c	Notes
Assessment of Sign and Symptoms (NYHA class)	X					X ^f								X	X	
12-Lead ECG	X							X						X		ECGs should be recorded after the participant has been supine for at least 5 minutes. On Day 1, ECG will be collected pre-dose and at hours 2, 4, and 8. On Day 8 and Day 14, it will only be collected pre-dose.
Concomitant Medication Use	X	X	X	X	X	X	X	X	X	X	X	X	X	X	X	
Central Laboratory Assessments																

Table 2-2: On-Treatment and Follow-up Procedural Outline (CV019010)

Procedure	Randomization D1 ^a	D 2	D 3	D 4	D 5	D 6	D 7 ^b	D 8 Visit ^c	D 9 ^b	D 10	D 11 ^b	D 12	D 13 ^d	D14 End of Study Visit c,d,e	D30 (± 2 days) Follow -Up Visit ^c	Notes
Hematology and Serum Chemistry ^h	X	X	X			X ^f		X						X	X	See Section 9.4.5 .
Urinalysis ^h	X	X	X			X ^f		X						X	X	See Section 9.4.5.

[figure not shown]

Table 2-2: On-Treatment and Follow-up Procedural Outline (CV019010)

Procedure	Randomization D1 ^a	D 2	D 3	D 4	D 5	D 6	D 7 ^b	D 8 Visit ^c	D 9 ^b	D 10	D 11 ^b	D 12	D 13 ^d	D14 End of Study Visit c,d,e	D30 (± 2 days) Follow -Up Visit ^c	Notes
Adverse Event Reporting																
Monitor for Non-Serious Adverse Events & Serious Adverse Events	X	X	X	X	X	X	X	X	X	X	X	X	X	X	X	
Pharmacokinetic (PK) Assessments																
Blood PK Sampling	See Table 9.5-1 for sampling schedule														See Section 9.5 .	

Table 2-2: On-Treatment and Follow-up Procedural Outline (CV019010)

Procedure	Randomization D1 ^a	D 2	D 3	D 4	D 5	D 6	D 7 ^b	D 8 Visit ^c	D 9 ^b	D 10	D 11 ^b	D 12	D 13 ^d	D14 End of Study Visit c,d,e	D30 (± 2 days) Follow -Up Visit ^c	Notes
Clinical Drug Supplies																
Randomize	X															
Study Drug Administration	X	X	X	X	X	X	X	X	X	X	X	X	X	X		IP is administered subcutaneously once daily.

Abbreviations: [redacted] BP = blood pressure; COVID-19 = coronavirus disease 2019; D = Day; [redacted] ECG = electrocardiogram; HF = heart failure; ICF = informed consent form; IMP = investigational medicinal product;

IP = investigational product; IV = intravenous; [REDACTED] NYHA = New York Heart Association; PE = physical examination; PK = pharmacokinetic [REDACTED].

- a If screening and randomization are on the same day all evaluations can be performed only once.

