5.1 Overall Design

This is a Phase 2A randomized, double-blind, placebo-controlled study of BMS-986259 in hemodynamically stabilized patients currently hospitalized for ADHF. The study is designed to establish if BMS-986259 is safe and well tolerated in this population with regards to clinically significant hypotension.

- ADHF must be the main reason for hospitalization, and other conditions with similar signs and symptoms must be excluded at screening.
- at least 24 hours after presentation to Emergency Room (ER) and no later than 8 days after presentation to ER. Time of the presentation is defined as the time of the first dose of IV diuretic in the hospital. Randomization must occur within a maximum of 8 days since presentation to ER and before hospital discharge.

- at least 12 hours since last dose change of IV loop diuretics and at least 24 hours since last dose of positive inotropes and ≥ 12 hours since the last dose of IV vasodilators.
- Prior to randomization, participants will also be tested for SARS-CoV-2 by reverse transcription polymerase chain reaction (RT-PCR) or rapid antigen test. Only participants with a negative test result are eligible for randomization.

Participants will be randomized 1:1 to receive BMS-986259 3 mg or placebo. Treatment will be administered subcutaneously once daily for 14 days and follow-up will last until Day 30 (± 2 days).

A minimum hospital stay of 5 days from randomization/first dose of IP is required. If participants are discharged home before the end of active study treatment, study visits will be performed daily either as an outpatient clinic visit or by a home nurse or healthcare provider (per local regulations/requirements) who will be responsible to measure pre-dose BP, draw PK sample(s), administer the IP subcutaneously

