7.4.1 Dose Down-titration

- On Days 1 through 6, if the participant experiences SBP < 85 mmHg without symptoms related to hypotension, the measurement must be repeated in 30 minutes. If the SBP remains < 85 mmHg the next day's study drug administration should be skipped and dosing should resume at 1 mg, the following day, if SBP is \geq 85 mmHg (ie, after a 1-day drug "holiday", the treatment will resume at a reduced dose).
- On Days 1 through 6, if the participant experiences SBP < 90 mmHg and symptoms of hypotension (such as dizziness, light headedness etc), the measurement must be repeated in 30 minutes. If the SBP remains < 90 mmHg the next day's study drug administration should be skipped and dosing should resume at 1 mg, the following day, if SBP is \geq 85 mmHg and symptoms of hypotension resolved (ie, after a 1-day drug "holiday", the treatment will resume at a reduced dose).
- On Days 1 through 6, if the participant experiences SBP fall \geq 40 mmHg with symptoms of hypotension that in the opinion of investigator preclude further safe dosing of the participant at the initial dose level, the next day's study drug administration should be skipped and dosing should resume at 1mg the following day, if SBP is \geq 85 mmHg and symptoms of hypotension resolved (ie, after a 1-day drug "holiday", the treatment will resume at a reduced dose).
- After dose reduction, the dose cannot be increased again.

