7.4.2 Permanent discontinuation of the study drug

- If the participant experiences SBP < 85 mmHg regardless of symptoms of hypotension, or symptomatic hypotension with SBP < 90 mmHg (measurements must be repeated in 30 minutes), despite dose reduction, then the study drug must be discontinued.
- On Days 7 through 14, if the participant experiences SBP < 85 mmHg regardless of symptoms of hypotension, the measurement must be repeated in 30 minutes. If the SBP remains < 85 mmHg, the study drug should be discontinued.
- On Days 7 through 14, if the participant experiences SBP < 90 mmHg and symptoms of hypotension (such as dizziness, lightheadedness, etc), the measurement must be repeated in 30 minutes. If the SBP remains < 90 mmHg, the study drug should be discontinued.

- Regardless of the day of the treatment, if the participant experiences SBP fall ≥ 40 mmHg with symptoms of hypotension, that in the opinion of investigator preclude further safe dosing of the participant, then the study drug should be discontinued.
- If the participant requires intravenous vasodilators, continuous IV diuretics or IV inotropes, the study drug should be discontinued

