9.2.2 Method of Detecting AEs and SAEs

AEs can be spontaneously reported or elicited during open-ended questioning, examination, or evaluation of a participant. Care should be taken not to introduce bias when collecting AE and/or SAEs. Inquiry about specific AEs should be guided by clinical judgement in the context of known AEs, when appropriate for the program or protocol.

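### Symptomatic SBP readings of 85–89 mmHg can escape the primary endpoint, because the confirming repeat depends on symptoms that no visible timed check records

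*Combined protocol and SAP*

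**What the plan says.** Table 4-1 gives the primary endpoint two limbs. Limb 1 is a confirmed supine SBP below 85 mmHg, whatever the symptoms. Limb 2 is a supine SBP below 90 mmHg "confirmed by repeat measurement within 30 minutes) AND symptoms of hypotension".

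The visible rules that require a repeat reading are in Section 7.4:

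- Days 1–6, below 85 mmHg: "SBP < 85 mmHg without symptoms related to hypotension, the measurement must be repeated in 30 minutes".
- Days 1–6, below 90 mmHg: "SBP < 90 mmHg and symptoms of hypotension (such as dizziness, light headedness etc), the measurement must be repeated in 30 minutes".
- Days 7–14: below 85 mmHg a repeat is required regardless of symptoms; below 90 mmHg the condition is again "SBP < 90 mmHg and symptoms of hypotension (such as dizziness, lightheadedness, etc), the measurement must be repeated in 30 minutes".

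On symptoms, the Vital Signs row of Table 2-2 gives times and position for blood pressure and no symptom item. The scheduled symptom row, "Assessment of Sign and Symptoms (NYHA class", falls on Day 1, discharge, Day 14 and Day 30. Adverse events are monitored daily from Day 1 to Day 14 and on Day 30. Section 9.2.2 says how they are found: "AEs can be spontaneously reported or elicited during open-ended questioning, examination, or evaluation of a participant". It leaves inquiry about specific events to clinical judgement.

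After discharge, the daily visitor is the person "who will be responsible to measure pre-dose BP, draw PK sample(s), administer the IP subcutaneously"; the visible list breaks off there. Participants receive a blood pressure device to use when they have symptoms. Section 5.1 and Section 9 tell them to report if SBP is below 85 mmHg on two readings and symptoms persist.

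**The concern.** Limb 2 needs three facts that belong to the same moment: a low reading, a second low reading within 30 minutes, and symptoms. At 85–89 mmHg the second fact is required only if the third is already known, and no visible procedure prompts for the third at the time of the reading. A repeat that was not taken cannot be recreated at analysis. A participant at 87 mmHg who is not asked, or who mentions light-headedness that evening, has no confirmation for that reading.

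Symptomatic hypotension is one of the two blood pressure events that Section 3.1 names as the purpose of the trial (the other is hypotension requiring discontinuation). Section 5.4 says the results will inform blood pressure margins for later studies. For a safety endpoint, lost events err towards reassurance.

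**Working it through.** **Step 1. Repeat rule against endpoint, by first reading.**

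| First SBP | Symptom status at the reading | Repeat required (7.4.1, 7.4.2)? | Consequence for the endpoint |
|---|---|---|---|
| <85 | any | yes | can be scored (limb 1) |
| 85–89 | recognised | yes | can be scored (limb 2) |
| 85–89 | asked, none | no | correctly not an event |
| 85–89 | not asked, or mentioned later | no | cannot be scored on this reading |
| 85–89 twice, self-measured at home | symptomatic | participant has two readings | has the limb 2 values, but no visible instruction to report |

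The last two rows are the gap. The fourth arises only because symptom status is not checked at the reading. The fifth arises because the participant's reporting threshold is 85 mmHg, 5 mmHg below that of limb 2.

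**Step 2. Where symptom status could come from.** NYHA class (Appendix 6) grades limitation of activity, fatigue, palpitation and dyspnea, not dizziness, and is scheduled on four occasions. Adverse event monitoring is daily but open-ended and not tied to a reading. A dizziness event learned of later supplies the symptom but not the repeat.

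**Step 3. The plan's own figure.** Section 10.1 uses N=60 (30 per arm) and gives a 5-fold increase at a placebo rate of 5% (25%) and a 2.7-fold increase at 15% (40.5%). It states no alpha, sidedness or power, so there is no single target to reproduce. With p̄ the mean of the two rates and SE0 = √[2p̄(1−p̄)/30]:

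- 5% v 25%: p̄ = 0.15, SE0 = 0.0922, z = 0.200/0.0922 = 2.17.
- 15% v 40.5%: p̄ = 0.2775, SE0 = 0.1156, z = 0.255/0.1156 = 2.21.

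Both exceed 1.96, so the folds fit an observed increase that would reach significance. With SE1 = √[(p1(1−p1)+p2(1−p2))/30], approximate two-sided 5% power is Φ[(difference − 1.96·SE0)/SE1]:

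- 5% v 25%: Φ[(0.200 − 0.1807)/0.0885] = 58.6%.
- 15% v 40.5%: Φ[(0.255 − 0.2266)/0.1108] = 60.1%.

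**Step 4. What a loss would do.** Let s be the share of events that qualify through limb 2 only and c the probability that such an event is captured, equal in both arms. Then observed rate = true rate × [1 − s(1 − c)]. The documents give neither s nor c. The ranges below (s 25–75%, c 90–50%) are assumptions.

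| s, c | Factor | 5% v 25% becomes | Risk difference | Power | 15% v 40.5% becomes | Risk difference | Power |
|---|---|---|---|---|---|---|---|
| no loss | 1.000 | 5.0% v 25.0% | 0.200 | 58.6% | 15.0% v 40.5% | 0.255 | 60.1% |
| 25%, 90% | 0.975 | 4.9% v 24.4% | 0.195 | 57.3% | 14.6% v 39.5% | 0.249 | 58.6% |
| 50%, 70% | 0.850 | 4.3% v 21.3% | 0.170 | 50.6% | 12.8% v 34.4% | 0.217 | 50.7% |
| 75%, 50% | 0.625 | 3.1% v 15.6% | 0.125 | 38.0% | 9.4% v 25.3% | 0.159 | 36.8% |

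The relative risk stays at 5.0 and 2.7 throughout, because the factor cancels. Expected events per 30 participants in the worst row are 0.9 and 4.7 instead of 1.5 and 7.5, or 2.8 and 7.6 instead of 4.5 and 12.2. The analysis is by estimation, so power serves here only as a gauge of lost precision.

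**The case against.** A reader might infer that nobody ever asks about symptoms. The documents do not support that. Adverse events are monitored daily, inquiry may target known risks, and Section 3.3 names hypotension as the principal risk. Symptoms trigger a home reading, and symptomatic hypotension triggers contact with the investigator. Applying Section 7.4 below 90 mmHg also presupposes that staff know the symptom status. What remains is narrower: none of these routes visibly ties a symptom answer to a reading.

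The conditional repeat is not wrong in itself. Limb 2 requires symptoms, so an asymptomatic 85–89 mmHg reading is properly a non-event. This point stands. The rule loses events only where symptom status was not established in time.

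A missed reading is not a missed participant. Readings continue four times daily in hospital and daily at home, and the participant can still qualify later. This also stands, and it makes the loss per participant smaller than the loss per reading.

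It is also tempting to say that the database cannot separate asymptomatic from not asked. The eCRF is not among the documents, and part of the home visit duties and of Table 2-2 is redacted, so that cannot be asserted. A suitable field may exist.

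Finally, prompted questions could raise reported symptoms and, through the existing rules, dose modifications. That is a real cost of the change.

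**Conclusion.** The point holds as a risk of under-capture that is inexpensive to remove. The text shows that the repeat at 85–89 mmHg depends on symptoms, that no structured check at the reading is visible, and that the post-discharge reporting threshold does not match limb 2. It does not show that events are in fact under-counted.

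The likely direction is lower absolute event rates and a smaller risk difference, both of which Section 10.3.2 reports, with less precision. A reader might infer a biased relative risk. With equal loss in both blinded arms it is unchanged in expectation, and nothing in the documents points to unequal loss. The relative fall of 2.5% to 37.5% in observed rates rests wholly on the assumed share and capture ranges; the true size is unknown.

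**What to change.** Add to the Vital Signs note in Table 2-2, for endpoint scoring only:

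- Every SBP below 90 mmHg is repeated within the endpoint's confirmation window, whether or not symptoms are known. This covers hospital, clinic and home nurse readings and recorded self-measured readings.
- Hypotension symptom status (yes/no, with time) is recorded at that reading on the eCRF, unless such a field already exists.

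Derive limb 2 from these fields and say so in the SAP. Reconcile the post-discharge reporting instruction in Sections 5.1 and 9 with limb 2 so that qualifying home readings reach the database; which clinical threshold applies is for the sponsor to settle. The wording of the Section 7.4 dose rules does not change.

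The cost is one schedule note, at most one eCRF item with its time, and a few extra cuff readings. Direct questioning may raise reported symptoms in both blinded arms, so absolute rates may look less favourable and more dose modifications may follow under the existing rules.

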5 STUDY DESIGN

[figure not shown]
5.1 Overall Design

This is a Phase 2A randomized, double-blind, placebo-controlled study of BMS-986259 in hemodynamically stabilized patients currently hospitalized for ADHF. The study is designed to establish if BMS-986259 is safe and well tolerated in this population with regards to clinically significant hypotension.

- ADHF must be the main reason for hospitalization, and other conditions with similar signs and symptoms must be excluded at screening.
- at least 24 hours after presentation to Emergency Room (ER) and no later than 8 days after presentation to ER. Time of the presentation is defined as the time of the first dose of IV diuretic in the hospital. Randomization must occur within a maximum of 8 days since presentation to ER and before hospital discharge.

- at least 12 hours since last dose change of IV loop diuretics and at least 24 hours since last dose of positive inotropes and ≥ 12 hours since the last dose of IV vasodilators.
- Prior to randomization, participants will also be tested for SARS-CoV-2 by reverse transcription polymerase chain reaction (RT-PCR) or rapid antigen test. Only participants with a negative test result are eligible for randomization.

Participants will be randomized 1:1 to receive BMS-986259 3 mg or placebo. Treatment will be administered subcutaneously once daily for 14 days and follow-up will last until Day 30 (± 2 days).

A minimum hospital stay of 5 days from randomization/first dose of IP is required. If participants are discharged home before the end of active study treatment, study visits will be performed daily either as an outpatient clinic visit or by a home nurse or healthcare provider (per local regulations/requirements) who will be responsible to measure pre-dose BP, draw PK sample(s), administer the IP subcutaneously

Participants will return for up to three ambulatory visits at the site on Day 8, Day 14, Day 30 (follow-up). If the participant cannot return to the site because of COVID-19 local regulations that prevent visits in-person, these visits can be done at home by the home nurse in discussion with the Principal Investigator (or designee). In addition, at discharge, participants will receive BP measuring device and will be instructed to measure BP if symptoms consistent with hypotension occur. If systolic BP falls below 85 mmHg (on 2 repeated measurements within 30 minutes) and symptoms of hypotension persist, participants will be instructed to report to the study site or another healthcare provider if the study site cannot be reached.

Initially participants with SBP ≥ 115 mmHg will qualify to be randomized 1:1 to receive 3 mg subcutaneous BMS-986259 QD or placebo. After approximately 8 participants with SBP ≥ 115 and < 130 mmHg have completed the treatment period, the Safety Review Committee will review the safety data from this sentinel group and ensure it is safe to proceed with the Main Group, ie., open the recruitment for participants with SBP less than 115 mmHg (but at least 100 mmHg).

The Main Group will include participants with SBP ≥ 100 mmHg, randomized 1:1 to BMS-986259 or placebo. The proportion of participants with SBP > 125 mmHg will be capped at 48 participants.

Study drug may be down-titrated to 1 mg or discontinued according to the criteria described in dose modification in [Section 7.4](#).

In addition, if systolic BP is < 85 mmHg or symptomatic hypotension occurs, the Principal Investigator (or designee; must be a medical doctor [MD]) must be contacted to make a decision

[figure not shown]

as to whether an ambulatory unscheduled study visit or hospitalization is required based on overall clinical assessment. For example, asymptomatic study participants who can walk and have normal urination may not require hospitalization. BMS Study Director/Medical Monitor (or designee) must be notified. A blinded clinical contact will be available 24/7 to answer questions and guide the home nurse as needed.

The study design schematic is presented in [Figure 5.1-1](#).

Figure 5.1-1: Study Design Schematic

Abbreviations: [REDACTED] D = day; ER = emergency room; [REDACTED] QD = once daily; R = randomization; SBP = systolic blood pressure.

^a May be down-titrated to 1 mg or discontinued according to the criteria described in Section 7.4.

^b Safety review of the sentinel group requires at least 8 participants with systolic blood pressure \geq 115 mmHg and $<$ 130 mmHg.

^c If participant is discharged before the end of active study treatment, study visits will be performed daily either as an outpatient clinic visit or by a home nurse or healthcare provider.

Physical examinations, vital sign measurements, 12-lead ECGs, and clinical laboratory evaluations will be performed at selected times throughout the dosing interval and during follow-up. Participants will be closely monitored for AEs throughout the study.

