Participants will be randomized 1:1 to receive BMS-986259 3 mg or placebo. Treatment will be administered subcutaneously once daily for 14 days and follow-up will last until Day 30 (± 2 days).

[REDACTED]

A minimum hospital stay of 5 days from randomization/first dose of investigational product (IP) is required. If participants are discharged home before the end of active study treatment, study visits will be performed daily either as an outpatient clinic visit or by a home nurse or healthcare provider (per local regulations/requirements) who will be responsible to measure pre-dose BP, draw PK sample(s), administer the IP subcutaneously [REDACTED] when appropriate per study schedule.

Participants will return for up to three ambulatory visits at the site on Day 8, Day 14, Day 30 (follow-up). If the participant cannot return to the site because of coronavirus disease 2019 (COVID-19) local regulations that prevent visits in-person, these visits can be done at home by the home nurse in discussion with the Principal Investigator (or designee). In addition, at discharge, participants will receive BP measuring device and will be instructed to measure BP if symptoms consistent with hypotension occur. If systolic BP falls below 85 mmHg (on 2 repeated measurements within 30 minutes) and symptoms of hypotension persist, participants will be instructed to report to the study site or another healthcare provider if the study site cannot be reached.

Initially participants with SBP ≥ 115 mmHg will qualify to be randomized 1:1 to receive 3 mg subcutaneous BMS-986259 once daily (QD) or placebo. After approximately 8 participants with SBP ≥ 115 and < 130 mmHg have completed the treatment period, the Safety Review Committee will review the safety data from this sentinel group and ensure it is safe to proceed with the Main Group, i.e., open the recruitment for participants with SBP less than 115 mmHg (but at least 100 mmHg).

[figure not shown]
The Main Group will include participants with SBP ≥ 100 mmHg, randomized 1:1 to BMS-986259 or placebo. The proportion of participants with SBP > 125 mmHg will be capped at 48 participants.

Study drug may be down-titrated to 1 mg or discontinued according to the criteria described in dose modification.

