9 STUDY ASSESSMENTS AND PROCEDURES

- Study procedures and timing are summarized in the Schedule of Activities ([Section 2](#)).
- Protocol waivers or exemptions are not allowed.
- All immediate safety concerns must be discussed with the Sponsor immediately upon occurrence or awareness to determine if the participant should continue or discontinue treatment.
- Adherence to the study design requirements, including those specified in the Schedule of Activities, is essential and required for study conduct.
- All screening evaluations must be completed and reviewed to confirm that potential participants meet all eligibility criteria before randomization. The investigator will maintain a screening log to record details of all participants screened and to confirm eligibility or record reasons for screening failure, as applicable.
- Procedures conducted as part of the participant's routine clinical management (eg, blood count) and obtained before signing of informed consent may be utilized for screening or baseline purposes provided the procedure meets the protocol-defined criteria and has been performed within the timeframe defined in the Schedule of Activities ([Section 2](#)).

- Blood pressure device will be provided to participants at discharge to measure BP if symptoms consistent with hypotension occur. If systolic BP falls below 85 mmHg (in 2 repeated measurements within 30 minutes) and symptoms of hypotension persist, participants will be instructed to report to the study site or another healthcare provider.

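### Participants at home are told to report a narrower set of low blood pressure episodes than the set that Section 7.4 says should change or stop dosing

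*Combined protocol and SAP*

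**What the plan says.** Three parts of the protocol bear on this.

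*What a discharged participant is told.* Under Section 5.1, participants get a BP device at discharge and "will be instructed to measure BP if symptoms consistent with hypotension occur". The rule for reporting to the site, or to another provider if the site cannot be reached, follows: "If systolic BP falls below 85 mmHg (on 2 repeated measurements within 30 minutes) and symptoms of hypotension persist, participants will be instructed". The Synopsis gives the same condition ("If systolic BP falls below 85 mmHg (on 2 repeated measurements within 30 minutes) and symptoms of hypotension persist"), as does Section 9 ("If systolic BP falls below 85 mmHg (in 2 repeated measurements within 30 minutes) and symptoms of hypotension persist"). Both elements are required: two readings below 85 mmHg, and symptoms that have not gone away.

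*What changes dosing.* Section 7.4.1 applies to Days 1-6. One of its triggers is "On Days 1 through 6, if the participant experiences SBP < 90 mmHg and symptoms of hypotension", confirmed at 30 minutes; another is confirmed SBP below 85 without symptoms. In either case the following day's injection is omitted and treatment restarts at 1 mg the day after, if recovery conditions are met. Section 7.4.2 applies the same thresholds from Day 7, and the response becomes discontinuation: "On Days 7 through 14, if the participant experiences SBP < 85 mmHg regardless of symptoms of hypotension" and "On Days 7 through 14, if the participant experiences SBP < 90 mmHg and symptoms of hypotension", each with a confirming reading.

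*What counts as an event.* The primary endpoint in Section 4 uses the same two limits for supine readings. Its symptomatic limb is "Supine SBP < 90 mmHg (confirmed by repeat measurement within 30 minutes) AND symptoms of hypotension"; the other limb is confirmed supine SBP below 85 with or without symptoms.

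Section 5.1 also has a broader rule. When SBP is under 85 or there is symptomatic hypotension, the investigator is to be contacted to decide between an unscheduled visit and hospitalization. It does not say who makes the contact.

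**The concern.** Section 3.3 names hypotension as the principal risk and relies on post-discharge BP monitoring and the dose-modification algorithm to control it. At home, that algorithm works only if a qualifying reading reaches the person who gives the next injection. A participant who follows the stated instruction exactly can have a reading that calls for a dose to be withheld or the drug stopped, and tell nobody.

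The main stake is safety: the next dose may be given when Section 7.4 says it should not be. From Day 7, the dose in question is one that should have been the first of a permanent stop.

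The second stake is ascertainment. A confirmed supine episode that stays with the participant is missing from the primary endpoint, and few events are expected.

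**Working it through.** The plan states no figure for this point, so there is nothing to reproduce. The check sets the rules side by side, followed by simple counts of exposure and sensitivity.

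**1. Rule comparison.** Participants are told to measure only when symptomatic, so each row starts with symptoms at home.

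| Episode | Section 7.4 dose rule | Section 4 endpoint, if supine | Told to report? |
|---|---|---|---|
| A. Both readings < 85, symptoms persist | Met | Met | Yes |
| B. Both readings < 85, symptoms have cleared | Met | Met | No |
| C. Both readings < 90, at least one of 85-89, with symptoms | Met | Met | No |
| D. Fall of 40 mmHg or more with symptoms, e.g. 140 to 98 | Met if the investigator judges further dosing unsafe | Not met | No |

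Every episode that triggers a report also meets the dose rule, but not the reverse: the home trigger is a strict subset. Rows B and C are the finding. Row D shows the same gap, but it depends on investigator judgement and the conclusion does not rest on it. The width of the symptomatic gap is 90 − 85 = 5 mmHg.

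**2. Could staff learn of rows B and C some other way?**
- The scheduled post-discharge BP (Table 2-2) is one pre-dose reading per day. A normal value does not show what happened hours earlier.
- AEs are monitored on every study day, but Section 9.2.2 describes spontaneous reports or open-ended elicitation. No visible text tells the visitor to ask for device readings.
- The 24/7 clinical contact in Section 5.1 is described as support for the home nurse.

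So staff learn of the reading only if the participant mentions it.

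**3. Time at home (upper bound).** Section 5.1 requires at least 5 hospital days, and footnote f of Table 2-2 puts discharge at Day 6 or later. Doses on Days 1-14 leave 14 − 1 = 13 between-dose intervals. With Day 6 discharge, those from Day 6-7 to Day 13-14 are at home:

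- 8 / 13 = 61.5%
- If the study ends on Day 13 (footnote d): 7 / 12 = 58.3%

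Later discharge lowers both. The Days 1-6 rule can apply at home in at most the first of these intervals; after that the required response is discontinuation.

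**4. Sensitivity of the endpoint.** Section 10.1 plans about 72 randomized (36 per arm), at least 60 completers (30 per arm if balanced), and a placebo rate of 5% to 15%.

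- One unreported event: 1/36 = 2.8 percentage points; 1/30 = 3.3 points
- Expected placebo events: 36 × 0.05 = 1.8; 36 × 0.15 = 5.4

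**The case against.** The strongest reply is that the home instruction is an attendance threshold, not a disclosure rule. Being told to go to the site or another provider reads naturally as seeking care in person, and a stricter limit for that than for a next-day dose change is no contradiction. The broader Section 5.1 rule already covers rows B and C, and its choice between an unscheduled visit and hospitalization makes sense mainly for people already discharged. A professional sees the participant before every home dose, and each reading in the gap follows a recent symptom that daily AE monitoring is meant to find. Harm therefore needs a participant who has symptoms, confirms a low reading on a device supplied for that purpose, and does not mention it at the next visit. Part of the home-nurse duties is redacted, and no participant or nurse manual is among the documents. Section 7.4 also leaves room for investigator judgement.

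Much of this stands. The daily visit is a real safeguard, the attendance reading is plausible, and unseen material may add a check. The objection does not supply a route for the reading. No other visible participant reporting instruction exists. The broader contact rule names no caller and is not said to be given to participants. The investigator cannot exercise judgement on an episode nobody has reported. It is also fair that the instruction is the same in both blinded arms and that no differential loss has been shown; none is claimed.

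**Conclusion.** The concern holds. The participant instruction is narrower than the Section 7.4 triggers in two ways: symptomatic confirmed SBP below 90 with a reading of 85-89, and confirmed SBP below 85 once symptoms have gone. A qualifying home reading may therefore not reach staff before the next dose. This should be fixed, mainly for safety. Confidence is medium, because the daily visit and unseen instructions may catch some episodes.

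The exposure is at most 8 of 13 between-dose intervals (62%), assuming Day 6 discharge. Against 1.8 to 5.4 expected placebo events, one lost event is worth 2.8 percentage points in an arm of 36. That applies only to supine readings. The documents give no frequency of unreported episodes, so neither the number of doses wrongly given nor any bias in the comparison can be stated.

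Wholly asymptomatic SBP below 85 between visits is outside this point, as is the choice to monitor more heavily in hospital while exposure is still rising, which Section 5.4 explains.

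**What to change.** Change the participant instruction in the Synopsis and Sections 5.1 and 9 to two tiers:

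- **Call the site before the next dose** for confirmed SBP below 85, whether or not symptoms continue, or confirmed SBP below 90 with symptoms.
- **Attend urgently** at the present threshold (confirmed below 85 with persisting symptoms).

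In Section 5.1, state that the participant calls the site and that the visiting nurse or site staff then contacts the investigator. Ask for supine self-measurement where feasible. Unless redacted text or existing forms already require it, have the daily visitor ask for and record, before injecting, any device reading, its repeat, body position and symptoms. Count only confirmed supine readings toward the primary endpoint and report the others separately.

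The cost is low: wording in three places and in the participant instruction, plus one question at a visit that already takes place. The downside is some extra calls and a little data entry. Recording position is necessary so that non-supine home readings do not enter the primary endpoint.
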